|--------------------------------------------------------------------|-------------------------------------------------------------------------------------------------------------------------------------------------------------------------------------------------------------------------------------------------------------------------------------------------------------------------------------------------------------------------|----------|
| Number of patients with antibodies to concizumab                   | Concizumab 
 
Before the pausec: From start of treatment (week 0b) up until 7 weeks after the treatment was paused
 
 
as well as
 
 
After the pausec: From start of concizumab treatment up until the end of trial (week 167)
 
 |          |
| Pharmacokinetic and pharmacodynamic endpoints               |                                                                                                                                                                                                                                                                                                                                                                         |          |
| Pre-dose (trough) concizumab plasma concentration ( $C_{trough}$ ) | Prior to the concizumab administration at week 24 (after restart)                                                                                                                                                                                                                                                                                                       | ng/mL    |
| Pre-dose thrombin peak                                             | Prior to the concizumab administration at week 24 (after restart)                                                                                                                                                                                                                                                                                                       | nmol/L   |

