## 8 Discontinuation/Withdrawal criteria

### 8.1 Discontinuation of trial treatment

The patient may be discontinued from trial product at any time during the trial at the discretion of the investigator for safety, behavioural, compliance or administrative reasons.

Efforts must be made so that patients, who discontinue trial product, attend and complete all scheduled visit procedures according to the flowchart in Section 2. Patients should stay in the trial irrespective of lack of adherence to the treatment, lack of adherence to visit schedule or missing assessments. Only patients who withdraw consent will be considered as withdrawn from the trial. Patients must be educated about the continued scientific importance of their data, even if they discontinue trial product.

The patient must be discontinued from trial product, if the following applies:

1. Included in the trial in violation of the inclusion and/or exclusion criteria
2. Simultaneous participation in another clinical trial of an approved or non-approved investigational medicinal product
3. Incapacity or unwillingness to follow the trial procedures
4. Significant thromboembolic eventa
5. Event of Disseminated Intravascular Coagulation (DIC)
6. Event of Thrombotic Microangiopathy (TMA)
7. Event of severe or serious hypersensitivity reaction related to concizumab

aThe definition of a significant thromboembolic events is provided in [Appendix 5](#). For venous thromboembolic events where treatment of concizumab has been discontinued, re-initiation of concizumab can be considered by the investigator in the extension part of the trial, after the patient has fully recovered. The investigator must contact and agree with Novo Nordisk before reinitiating concizumab treatment.

See the flowchart in Section 2 for data to be collected at the time of treatment discontinuation and follow-up and for further evaluations that need to be completed.

The primary reason for discontinuation of trial product must be specified in the end-of-treatment-form in the eCRF, and final drug accountability must be performed. A treatment discontinuation session must be made in the IWRS.

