#### 8.1.1 Temporary discontinuation of concizumab in relation to COVID-19

Regular testing for COVID-19 will not be part of the protocol, but will be done at the investigator's discretion only. Testing should be performed according to the locally recommended testing methodology.

In case a patient is tested positive for ongoing COVID-19 infection prior to the first concizumab dose, then visit 2a/9a (allocation/randomisation visit) should be postponed until a negative COVID-19 result exists or the patient has fully recovered from the COVID-19 infection as judged by the investigator. During the trial, in the case a patient is tested positive for ongoing COVID-19, concizumab should be paused immediately and not restarted until the patient tests negative again or has fully recovered from COVID-19 as judged by the investigator. In the interim period, patients should be treated as per judgement of the investigator.

If access to COVID-19 testing is limited, then the pause and postponement should be based on a strong suspicion, as judged by the investigator.

A positive COVID-19 test, or suspicion of COVID-19, is considered an AE and should be reported as such following the procedures in Section [9.3](#) and [Appendix 5](#).

In case of a suspected thromboembolic event, it is encouraged to perform a COVID-19 test. If a thromboembolic event is diagnosed, COVID-19 testing must be performed. Additionally, analysis for COVID-19 antibodies may be performed; see Section [9.4.6](#).

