## **9.2.2 Treatment with concizumab**

For in-between visit administrations of trial drug, patients will self-administer concizumab and will record their treatment in the eDiary which will be reviewed at each visit by trial site staff in StudyWorks and periodically by the sponsor staff.

In addition, the following items will be recorded in the eCRF at scheduled visits:

- Injection site location for the last dose taken prior to visit
- Time of last dose the day before the visit

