#### **9.5 Pharmacokinetics**

Concizumab will be quantified using a validated ELISA assay. Recombinant human TFPI will be used to capture concizumab. A colorimetric detection signal is obtained by the enzymatic reaction of horseradish peroxidase labelled anti-human IgG4 specific antibodies with the chromogenic substrate TMB (3,3',5,5'-tetramethylbenzidine). The amount of anti-TFPI present in the calibration, quality control and test samples correlate with the obtained signal strength.

Validation of the assay follows current guidelines for bioanalytical method validation. Bioanalytical data will be reported in a bioanalytical report.

The concizumab ELISA will be used to evaluate exposure and pharmacokinetics of concizumab.

For patients dosed with concizumab from visit 2a (patients in arms 2, 3 and 4), two 24-hour PK/PD-sessions will be conducted at visits 2a and 9a. The concizumab dose will be administered in the abdomen and blood samples will be drawn pre-dosing, 3, 6, 9 and 24 hours after dosing. Care must be taken to ensure the 24-hour sample is drawn before the next daily dose of concizumab is administered. At the day of visit 9a patients should not dose themselves at home; the dose will be administered at site followed by blood sampling. The dose should be taken at site in the abdomen and care must be taken to ensure the 24-hour sample is drawn before the next daily dose of concizumab is given.

For patients who had a 24-hour PK profile measured at visit 2 prior to the treatment pause, a new 24-hour PK profile at visit 2a should not be conducted after restart of the trial. For these patients, only pre-dose and 24-hour post-dose samples should be taken at visit 2a. Care must be taken to ensure the 24-hour sample is drawn before the next daily dose of concizumab is administered.

Following items must be recorded in the eCRF:

- Time of lab samples taken
- Time of concizumab dose
- Injection site location

See Section [2.1](#) for the specific timepoints for the PK analysis.

In addition to the two PK/PD sessions, pre-dose concizumab levels ( $C_{trough}$ ) will be measured throughout the concizumab treatment period. These blood samples must be drawn prior to trial product administration as specified in the flowchart in Section [2](#). If the patient has taken the daily

dose of concizumab before collection of the concizumab ELISA sample, then visit 4a (arm 2, 3, 4) and visit 9a.2 (arm 1) should be rescheduled.

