	
For subjects in arms 2-4 that are only exposed to the initial concizumab dosing regimen, the period begins at the time of start of the initial concizumab PPX regimen.
 
For subjects in arms 2-4 that start on the new concizumab dosing regimen and who have been exposed to the initial dosing regimen, the period consists of two periods with a pause in between. The first period begins at the time of start of the initial concizumab PPX regimen and ends 7 weeks after the treatment was paused while the second period begins at the time of start of the new concizumab PPX regimen.
 
For all cases of arms 2-4 above the periods end at the first occurrence of:
 

• Items 2., 3., 4., 5. or 6. above

On-treatment without data on initial regimen	
The time period where subjects are considered to be affected by on-demand treatment or treatment with the new concizumab dosing regimen.
 
The analysis data set is defined similarly as the ‘on-treatment’ analysis data set with the exception:
 

• Observation time during the initial concizumab PPX regimen is excluded

On-treatment without ancillary therapy a excl. data on initial regimen for subjects exposed to both regimens	
The time period where subjects are treated by either the new concizumab dosing regimen or the initial concizumab dosing regimen (only included if not exposed to the new concizumab dosing regimen) or are treated by on-demand treatment and additionally have not used factor-containing products not related to treatment of a bleed during any of the cases.
 
The analysis data set is defined similarly as the ‘on-treatment’ analysis data set with the exception:
 

• Periods where factor containing products not related to treatment of a bleed have been used are excluded

• For subjects in arms 2-4 that start on the new concizumab dosing regimen and who have been exposed to the initial dosing regimen, the data on the initial concizumab PPX regimen are excluded

a Ancillary therapy is defined as use of factor-containing products not related to treatment of a bleed.

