**Table 1 Analysis sets used for analyses and/or presentations of endpoints/assessments**

Endpoint/assessment categories a	Subject Analysis Set	Analysis Data Sets
Bleeding episodes	FAS	On-treatment without ancillary therapy excl. data on initial regimen for subjects exposed to both regimens
PK, PD and safety not relating to events	SAS	On-treatment without data on initial regimen
Safety relating to events b	SAS	On-treatment and On-treatment without data on initial regimen

aWhich endpoints/assessments that belong under each category can be found in section 9 of the protocol version 7.

bThis specifically refers to: number of thromboembolic events, number of hypersensitivity type reactions, number of injection site reactions, number of patients with antibodies to concizumab, and number of adverse events.

For arms 2-4 the target joints registered at baseline will be used for the assessment done at week 56. For arm 1 the target joint evaluation done at visit V9a will be used for assessment at week 56.

Continuous endpoints/assessments will be presented using descriptive statistics which will include min, max, mean, SD, median, and quartiles. For PK endpoints/assessments, the descriptive statistics will also include geometric mean and geometric CV. Event data (including AEs) will be summarised including number of subjects with an event/episode, percentage of subjects with an event/episode, number of events/episodes and rate of events/episodes. Categorical assessments will be summarised by number and percent of subjects in each category. Presentations of results will be by arm and visit (when applicable) and when relevant arm 1 will be split into two parts with on-demand treatment and concizumab treatment.

Baseline for the assessments done at week 56 is defined as the latest non-missing measurement recorded before the time of the first administration of concizumab with the new dosing regimen (arms 2-4 and arm 1 after receiving concizumab) or recorded before randomisation to the on-demand administration (arm 1). If this measurement is missing for arms 2-4 or a subject from arms 2-4 chooses not to restart on concizumab, then the baseline obtained prior to the initial dosing regimen will be used (if available). If the V9a measurement is missing for arm 1 concizumab part,

the latest measurement recorded prior to V9a will be used as a concizumab baseline for arm 1 subjects.

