Assessment	Number of treated spontaneous and traumatic target joint bleeds	
On demand (arm 1)
 
 
From randomisation (week 0) up until start of concizumab treatment (at least 24 weeks)
 
 
Concizumab (arm 1)
	Count	
Week 56 cut-off is when all patients from arm 2-4 have completed visit 13a assessments or permanently discontinued treatment.
 
Concizumab (arm 1) data available up until week 56 cut-off will be presented.
	5.5.1

		
 
From start of the new concizumab dosing regimen up until week 56 cut-off
 
 
Concizumab (arms 2-4)
 
 
From start of the new concizumab dosing regimen (week 0) up until week 56 cut-off
 
			
Assessment	The number of all spontaneous and traumatic bleeds (treated and untreated)	
On demand (arm 1)
 
 
From randomisation (week 0) up until start of concizumab treatment (at least 24 weeks)
 
 
Concizumab (arm 1)
 
 
From start of the new concizumab dosing regimen up until week 56 cut-off
 
 
Concizumab (arms 2-4)
 
 
From start of the new concizumab dosing regimen (week 0) up until week 56 cut-off
 
	Count	
Week 56 cut-off is when all patients from arm 2-4 have completed visit 13a assessments or permanently discontinued treatment.
 
Concizumab (arm 1) data available up until week 56 cut-off will be presented.
	5.5.1
Assessment	Pre-dose concizumab plasma concentration	
Concizumab (arms 2-4)
 
 
From start of the new concizumab dosing
 
	ng/mL	Summary of pre-dose assessments from start of the new concizumab dosing regimen (week 0) up until week 56.	5.5.2

		regimen (week 0) up until week 56 cut-off			
Assessment	Thrombin peak	At visits where thrombin generation assessments are planned to be measured in the trial up to 56 weeks	nmol/L	Summary of these assessments up until week 56.  From start of the new concizumab dosing regimen (week 0) up until week 56.	5.5.2
Assessment	Free TFPI concentration	At visits where free TFPI assessments are planned to be measured in the trial up to 56 weeks	ng/mL		5.5.2

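### The 56-week SAP lets samples from pauses, and from up to 7 weeks after the last dose, into the concizumab trough and PD summaries

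*Protocol*

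**What the plan says.** **56-week SAP.** Table 1 in section 5.1 assigns the category "PK, PD and safety not relating to events" to the safety analysis set and to the on-treatment data set with initial-regimen time removed. Section 4 describes that data set as "The time period where subjects are considered to be affected by on-demand treatment or treatment with the new concizumab dosing regimen". It is built like the general on-treatment set, and its one stated exception removes time on the initial regimen. The general set's start and end rules are introduced for safety endpoints that count events. For concizumab treatment the period ends at the earliest of 7 weeks after the last dose, the last site contact at or before the cut-off, withdrawal, loss to follow-up, or death.

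Appendix 2 (section 6.2) asks for a summary of pre-dose concentrations from week 0 to week 56. The thrombin generation rows are timed only by schedule: "At visits where thrombin generation assessments are planned to be measured in the trial up to 56 weeks". The free TFPI row is timed the same way. None of these PD rows says pre-dose.

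**Protocol.** Section 4.3.2.2 times the week-24 trough, thrombin peak and free TFPI as "Prior to the concizumab administration at week 24 (after restart". Section 9.5 places trough sampling within the concizumab treatment period and says of visit 9a that "the dose will be administered at site followed by blood sampling". Section 8.1 wants patients who stop trial product to "attend and complete all scheduled visit procedures according to the flowchart in Section" 2. Section 8.1.1 says that after a positive COVID-19 test "concizumab should be paused immediately and not restarted until the patient tests negative again", or has recovered in the investigator's judgement. Section 9.2.2 has the eCRF record "Time of last dose the day before the visit", and the eDiary holds home dosing.

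**The concern.** A 7-week tail suits adverse events, where carry-over of effect matters. It does not suit the trough of a daily regimen, since a sample weeks after the last dose says nothing about exposure on that regimen. An interruption does not close the period at all, because the 7 weeks run from the final dose.

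The label pre-dose does not screen these samples out. The flowchart footnote only forbids injecting on the visit day before sampling, and a patient who is off drug meets that automatically.

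At stake is the trial's description of exposure and PD on the new regimen. Protocol section 5.6 says exposure on the previous regimen was higher than expected. A summary that errs low is the less cautious error in that setting.

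**Working it through.** The plan states no figure for this point, so there is nothing to reproduce directly. One input can be checked: 42/(1 − 0.17) = 50.6, which rounds up to the 51 planned patients (protocol section 10.1).

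**1. How many post-stop samples the 7-week rule admits.** In arms 2–4 the flowchart schedules concizumab ELISA after the first dose at weeks 1, 4, 8, 12, 16, 20, 24, 28, 32, 40, 48 and 56. For each possible last-dose day from 1 to 391, count the later scheduled visits, and those no more than 49 days after the last dose.

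- Remaining scheduled visits: mean 5.14.
- Of these, inside the window: mean 1.34, range 0–2. That is 26%, so about 74% are already excluded.
- Last dose before week 24: 1–2 samples admitted (mean 1.8). Last dose from week 24 to week 56: 0–2 (mean 1.0).

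Example: with a last dose on day 150, weeks 24 and 28 are admitted, and weeks 32, 40, 48 and 56 are not.

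**2. Possible share at one visit.** Take week 24 as an example and assume discontinuation uniform over 32 weeks with total d. A sample from a stopped patient is inside the window if the last dose fell on days 119–167.

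Share = (7d/32) / (1 − 24d/32 + 7d/32)

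| d | 7d/32 | 24d/32 | Share |
|---|---|---|---|
| 5% | 1.09% | 3.75% | 1.1% |
| 10% | 2.19% | 7.50% | 2.3% |
| 17% | 3.72% | 12.75% | 4.1% |

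The 17% is the ceiling in protocol section 10.1. It was set for arms 1 and 2 and also counts withdrawals, whose period ends at the withdrawal date, so it overstates this source. Interruptions add to the share by an amount the documents do not give. A range of 1–5% is used below.

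**3. Effect on the summaries.** Let f be the off-dosing share and r the off-dosing level relative to the on-dosing trough. No half-life is given, so r from 0.5 to 0.01 is an assumption.

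- Geometric mean is multiplied by r^f.
- Arithmetic mean falls by f(1 − r).
- Log-variance rises by f(1 − f)(ln r)². Geometric CV = √(exp(log-variance) − 1). An assumed on-dosing log-SD of 1 gives a starting CV of 131%.

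| f | r | Fall in geometric mean | Fall in arithmetic mean | Geometric CV |
|---|---|---|---|---|
| 1% | 0.5 | 0.7% | 0.5% | 132% |
| 1% | 0.01 | 4.5% | 1.0% | 153% |
| 2% | 0.1 | 4.5% | 1.8% | 142% |
| 5% | 0.5 | 3.4% | 2.5% | 133% |
| 5% | 0.1 | 10.9% | 4.5% | 158% |
| 5% | 0.01 | 20.6% | 5.0% | 254% |

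Results are shown by arm. Arm 2 has 18 + 16 = 34 patients (protocol Table 2), so one such sample at a visit gives f = 1/34 = 2.9%. The geometric mean then falls by 2.0% at r = 0.5, 6.5% at r = 0.1 and 12.7% at r = 0.01.

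**4. Median.** If every off-dosing value lies below the median, the reported median is the on-dosing quantile (0.5 − f)/(1 − f). That is the 49.5th percentile at f = 1% and the 47.4th at f = 5%.

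**The case against.** A reader might infer that the SAP accepts every scheduled sample, whether or not the patient is dosing. It does not. Table 1 restricts PK and PD to an on-treatment period, and the 7-week limit already removes about three quarters of scheduled post-stop samples.

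A reader might also infer that the protocol's week-24 endpoints have the same defect. The documents do not support that. Section 4.3.2.2 ties the value to an administration, section 9.5 has that dose given on site in arms 2–4, and a patient who has stopped for good has none. The analysis sits in the SAP for the primary cut-off, which is not provided. One question remains: a patient resuming at visit 9a after an interruption would still satisfy the wording.

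Further points stand:

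- The off-dosing levels and the log-SD are assumptions.
- The geometric mean and CV apply to PK only.
- The median and quartiles are reported as well.
- The SAP's rule for values below the quantification limit covers only plots and AUC. If such values are left out of the tables, the effect is nearer the lower end.
- Planned post-dose PD samples are confined to the visit 2a and 9a sessions, and protocol Appendix 2 says laboratory samples are pre-dose, so the missing label on the PD rows matters less than it may seem.
- Section 8.1.1 does not state that visits continue during a pause. Equally, nothing suspends the schedule or excludes such samples.
- The evaluation is descriptive, and dose adjustment uses the individual visit 4a/9a.2 result.
- Derivation details are deferred to a reviewer's guide, which might contain a rule.

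None of this removes the gap. The SAP as written admits the tail and the interruptions, and the choice of data set belongs in the SAP.

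**Conclusion.** The concern holds as a limited point about the 56-week SAP. Its PK/PD data set takes over an end rule made for safety events and has no rule for interruptions, so off-dosing samples can enter the by-visit trough and PD summaries. The direction is clear: concentration geometric mean down, geometric CV up, and PD values toward untreated levels.

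The size is conditional. It is about 0.7–21% on the geometric mean for an off-dosing share of 1–5% at 50% to 1% of the on-dosing trough, with a median shift of at most about 2.6 percentile points. No single figure within that range is supported, because the documents give neither the share nor the level. No confirmatory conclusion and no patient's dose depends on these tables. The change is still worth making, because it is cheap and concerns the description of exposure on the revised regimen.

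**What to change.** - **SAP section 4 and Table 1:** give PK and PD their own data set, with start and end rules written out. It should end at the last dose and exclude temporary interruptions.
- **SAP section 5.5.2:** define a valid on-dosing sample by a pre-specified maximum time since the last recorded concizumab dose, from the eCRF item and eDiary in protocol section 9.2.2. Choose a limit that admits the trough taken just after the last dose. A flat requirement of a dose the day before would drop every patient with one missed dose and shift the table toward perfect adherence.
- **Week 0:** keep the pre-dose sample as baseline, outside this rule.
- **Appendix 2:** add pre-dose to the thrombin generation and free TFPI rows.
- **Reporting:** list off-dosing samples separately, and give an all-samples summary as a sensitivity. State how values below the quantification limit enter the tables.
- **Week-24 endpoints:** confirm that the primary-cut-off SAP applies the same rule.

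The cost is one derivation and a few sentences, with no new data. The downside is that a few samples leave the main table, which then describes exposure while dosing.
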